Hematocrit Hemoglobin RBC count WBC count Neutrophils Bands Lymphocytes Monocytes Basophils Eosinophils Platelet count	Blood Urea Nitrogen (BUN) Creatinine Total bilirubin INR (reflex only) ^c Albumin AST ALT Alkaline phosphatase CPK Sodium Potassium Bicarbonate/CO ₂ Chloride Calcium Inorganic phosphate Uric acid Total protein Glucose Cholesterol LDL-C HDL-C Triglycerides	Specific gravity Ketones pH Protein Glucose Blood Urobilinogen Bilirubin Leukocytes Nitrites Microscopic examination, if needed	Central Lab Tests: Serum Pregnancy (bHCG) test ^d ANA/reflex anti-dsDNA ^e HBsAg ^e HBsAb ^e HBv DNA PCR reflex only ^e HCV Ab ^e HCV RNA reflex only ^e Rheumatoid Factor ^e Anti-CCP antibodies ^e QuantiFERON-TB Gold ^f hs-CRP ^g FSHi ^h beta-D-glucan ⁱ HIV Ab ^j Local Lab Tests: Urine pregnancy test ^k ESR Varicella antibody, if indicated

[figure not shown]
- a. Minimum 8-hour fast. If a subject is not able to fast when necessary, due to unforeseen circumstances, the non-fasting status will be recorded in study source documentation.
- b. A urine dipstick macroscopic urinalysis will be completed by the central laboratory at all required visits. A microscopic analysis will be performed in the event the dipstick results show leukocytes, nitrite, protein, ketones, or blood greater than negative or glucose greater than normal.
- c. INR will only be measured if ALT and/or AST $> 3 \times$ ULN. A separate blood sample for INR testing will be needed to measure INR at the time of repeat testing for ALT or AST.
- d. A serum pregnancy test will be performed for all female subjects of childbearing potential at the Screening Visit and if any post-baseline urine pregnancy is positive.
- e. At Screening only. For subjects in China and Japan, or where mandated by local requirements: for subjects with HBs Ab+ and/or HBc Ab+ and negative HBV DNA at Screening, the HBV-DNA PCR test should be performed again every 12 weeks. Retesting every 12 weeks is not necessary with subjects that have a history of HBV vaccine and is HBs Ab+ and HBc Ab-.
- f. All subjects will be assessed for evidence of increased risk for TB by a risk assessment form (Appendix E) and tested for TB infection by QuantiFERON-TB Gold test analyzed by the central laboratory. The PPD Skin Test should be utilized only when an IGRA is not possible for any reason (unless both tests are required per local guidelines).

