- A negative test result for HBc Ab does not require HBV DNA PCR qualitative testing and the subject may be enrolled (Figure 2, Scenarios A and B). For a subject who has had a HBV vaccination (should document in the medical history), the HBV DNA PCR qualitative testing is not required and the subject may be enrolled. For subjects without a history of HBV vaccination (and where mandated by local requirements) a positive result for HBs Ab requires HBV DNA PCR testing (automatic reflex testing). (Figure 2, Scenario B).*
- A positive test result for HBc Ab requires HBV DNA PCR testing (automatic reflex testing) (Figure 2, Scenarios C and D).
 - A positive result for HBV DNA or a result that exceeds detection sensitivity will be considered positive and will be exclusionary. A subject with a negative result for HBV DNA may be enrolled.
 - For China, Japan and South Korea, or where mandated by local requirements: subjects with HBs Ab+ and/or HBc Ab+ and negative HBV DNA at Screening, should have HBV-DNA PCR testing performed approximately every 12 weeks. Retesting every 12 weeks is not necessary

when a subject has a history of HBV vaccine and are HBs Ab+ and HBc Ab-. If necessary, HBV-DNA PCR may be tested at unscheduled visits.

[figure not shown]
Figure 2. Interpretation and Management of HBV Serologic Test Results

- * For subjects who have had a HBV vaccination (should be documented in the medical history), a positive test result for HBs Ab is expected and these subjects may be enrolled. For subjects without a history of HBV vaccination (and where mandated by local requirements. a positive result for HBs Ab requires HBV DNA PCR testing.
- ** For China, Japan and South Korea, or where mandated by local requirements; subjects with HBs Ab+ and/or HBc Ab+ and negative HBV DNA at screening should have HBV DNA PCR testing performed approximately every 12 weeks. HBV DNA PCR testing every 12 weeks is not necessary when the subject has a history of HBV vaccine and is HBs Ab+ and HBc Ab-. If necessary, HBV DNA PCR may be tested at unscheduled visits.

Hepatitis C:

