Appendix C. Study Activities

[figure not shown]
Activity	SCR D -35 to D -1	BL D	Wk 2 D 15	Wk 4 D 29	Wk 8 D 57	Wk 12 D 85	Wk 16 D 113	Wk 20 D 141	Wk 24 D 169	Wk 28 D 197	Wk 32 D 225	Wk 36 D 253	Wk 44 D 309	Wk 56 D 393	Wk 68 ^a to Wk 248 (Every 12 Wks) D 477 to D 1737	Wk 260 or PD D 1821	30 Day F/U Visit/ Call ^b D 1851	70- Day F/U Call ^b D 1877
Informed Consent ^c	X																	
Inclusion/Exclusion Criteria	X	X																
CASPAR Criteria	X																	
Medical/Surgical History ^d	X	X																
Vital Signs ^e /Weight/Height ^f	X	X	X	X	X	X	X	X	X	X	X	X	X	X	X	X	X	
Alcohol/Nicotine Use	X																	
Prior/Concomitant Therapy ^g	X	X	X	X	X	X	X	X	X	X	X	X ^g	X	X	X	X	X	
Physical Exam ^h	X	X							X					X	X^h	X		
12-Lead ECG	X ⁱ													X	X ⁱ			
															Yearly, only if required by local regulations			
Chest X-Ray ^{k,1}	X^k													X^{l}	X^{l}	X ^l		
Bilateral X-Rays of Hands and Feet ^{m,n}	X ^{m, n}						X ^m		X ^m					X ^m	X ^m	X ^m		
Serum Pregnancy Test at Central Lab ^o	X																	
Local Urine Pregnancy Test ^{p,q}		X	X	X	X	X	X	X	X	X	X	X^q	X^q	X^q	X^q	X	X	
Latent TB Risk Factor Questionnaire ^r	X													X	X^{r}	X		

ABT-494 M15-572 Protocol Amendment 8 EudraCT 2016-004130-24

Activity	SCR D -35 to D -1	BL D 1	Wk 2 D 15	Wk 4 D 29	Wk 8 D 57	Wk 12 D 85	Wk 16 D 113	Wk 20 D 141	Wk 24 D 169	Wk 28 D 197	Wk 32 D 225	Wk 36 D 253	Wk 44 D 309	Wk 56 D 393	Wk 68 ^a to Wk 248 (Every 12 Wks) D 477 to D 1737	Wk 260 or PD D 1821	30 Day F/U Visit/ Call ^b D 1851	70- Day F/U Call ^b D 1877
Central Lab QuantiFeron TB Gold Test (and Local PPD Skin Test if Required) ^s	X													X	X ^s	X ^s		
Central Lab Tests ^t hs-CRP ^u Clinical Chemistry ^v Hematology (CBC) ^v Urinalysis ^w FSH ^x	X	X	X	X	X	X	X	X	X	X	X	X	X	X	X	X	X^{hh}	
Central Lab Test ^t Total Cholesterol HDL-C LDL-C Triglycerides		X		X		X			X									
ESR (Local Lab)	X	X	X	X	X	X	X	X	X	X	X	X	X	X	X	X	X	
Other Central Lab Tests HIV Screening ^j Hepatitis B ^y and C Screening Rheumatoid Factor Anti-CCP Antibodies ANA/Reflex Anti-dsDNA	X					X ^y			X ^y			X ^y			X ^y	X ^y		
Blood Samples for upadacitinib PK Assay ^{Z,aa}			X ^z	X ^z	X ^{aa}	X ^{aa}	X ^{aa}	X ^{aa}	X ^{aa}		X ^{aa}			X ^{aa}		X ^{aa}		

ABT-494 M15-572 Protocol Amendment 8 EudraCT 2016-004130-24

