- w. A urine dipstick macroscopic urinalysis will be completed by the central laboratory at all required visits. A microscopic analysis will be performed in the event the dipstick results show leukocytes, nitrite, protein, ketones, or blood greater than negative or glucose greater than normal.
- x. FSH should be tested at Screening if the female subject is < 55 years of age AND has had no menses for ≥ 12 months AND has no history of permanent surgical sterilization (defined in Section 5.2.4).
- y. For China, Japan and South Korea, or where mandated by local requirements: for subjects with HBs Ab+ and/or HBc Ab+ and negative HBV DNA at Screening, the HBV-DNA PCR test should be performed again approximately every 12 weeks. Retesting approximately every 12 weeks is not necessary for subjects that have a history of HBV vaccine and HBs Ab+ and HBc Ab-. If necessary, HBV DNA PCR may be tested at unscheduled visits.
- z. At Week 2 and Week 4 visits, PK samples should be collected prior to oral study drug dosing and the subjects should take the study drug dose at the clinic after collecting the PK blood sample. However, if the subject normally takes the study drug dose at a time that is after the time of the scheduled study visit, the subject should follow the regular dosing schedule and the PK sample should be collected at any time during the visit.

M15-572 Protocol Amendment 8 EudraCT 2016-004130-24

- aa. PK samples should be collected at any time during the visit. Subject should follow the regular dosing schedule. Collect PK samples at Week 8, Week 12, Week 16, Week 20, Week 24, Week 32, Week 56, and at PD visit only for subjects who prematurely discontinue from study drug treatment prior to Week 56. No PK sample collection is required at Week 260.
- bb. Prior to other study visit procedures.
- cc. PASI, BSA-Ps, sIGA, and SAPS are to be done at Week 80, Week 104, Week 128, Week 152, Week 176, Week 200, Week 224, Week 248 (every 24 weeks after the Week 56 visit) and at the final study visit (Week 260).
- dd. Collect serious adverse events and protocol-related non-serious AEs that occur after a subject signs the informed consent; prior to the first dose of study drug.
- ee. At Week 24, all placebo subjects will be switched to blinded upadacitinib regardless of clinical response.

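### The Appendix C grid leaves 32 weeks with no marked HBV DNA test where its own footnote asks for one about every 12 weeks; separately, the retest country list and the entry PCR rule need reconciling

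*Protocol*

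**What the plan says.** **Retest interval.** Protocol Section 5.3.1.1 (Hepatitis Screening) says that covered subjects "should have HBV-DNA PCR testing performed approximately every 12 weeks". Appendix C footnote y repeats this: "the HBV-DNA PCR test should be performed again approximately every 12 weeks". Both exempt subjects with a history of HBV vaccination who are HBs Ab+ and HBc Ab-. Both also allow HBV DNA PCR at an unscheduled visit if necessary.

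**Schedule.** The Appendix C row for other central laboratory tests carries footnote y on its label ("HIV Screening ^j Hepatitis B ^y and C Screening"). It has a mark at Screening and footnote y marks at Week 12, Week 24, Week 36, the Week 68 to Week 248 block and Week 260/PD. The Week 44 and Week 56 cells are empty.

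**Countries.** Footnote y reads "For China, Japan and South Korea, or where mandated by local requirements: for subjects with HBs Ab+ and/or HBc Ab+ and negative HBV DNA". Table 2 footnote e reads "For subjects in China and Japan, or where mandated by local requirements: for subjects with HBs Ab+ and/or HBc Ab+ and negative HBV DNA".

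**PCR at entry.** In Section 5.3.1.1 the bullet on core-antibody-negative subjects opens with "A negative test result for HBc Ab does not require HBV DNA PCR qualitative testing and the subject may be enrolled". It then says that in subjects without a vaccination history, with a parenthesis about local mandates, "a positive result for HBs Ab requires HBV DNA PCR testing". Exclusion criterion 5 (Section 5.2.2) attaches PCR in surface-antibody-positive subjects to China, Japan, South Korea or a local mandate, and does not mention vaccination.

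**The concern.** The visit grid is a document that sites can be expected to work from, and here it contradicts the footnote attached to the same row. The periodic HBV DNA test is a safety check in antibody-positive subjects taking study drug. The unmarked stretch begins at Week 36, when Section 5.2.3.2 first allows corticosteroids and non-biologic DMARDs to be started or changed outside rescue.

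The other route to an HBV DNA test is the ALT/AST trigger in Table 4, which is written for HBc Ab+ subjects only. A covered subject who is HBs Ab+ and HBc Ab- and unvaccinated therefore has no marked PCR and no HBV-specific trigger in that stretch. What remains is the footnote itself and the general ALT/AST rules.

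The country list and the entry rule matter for a different reason. Sites reading different parts of the protocol could reach different answers on who is retested and on who needs PCR before enrolment.

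**Working it through.** **1. Reading the grid.** The row has 18 visit columns. Counting cells puts the footnote y marks at Weeks 12, 24, 36, 68 to 248 (every 12 weeks per footnote a) and 260/PD. The same count applied to the hand and foot x-ray row gives Screening, Weeks 16, 24, 56, the Week 68 to 248 block and Week 260/PD. That agrees with footnote m, so the columns are aligned.

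**2. Intervals.** Marks after baseline: 3 (Weeks 12, 24, 36) + 16 (Weeks 68 to 248) + 1 (Week 260) = 20, hence 19 intervals. Eighteen are 12 weeks, which reproduces the interval in the text. One is not.

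- Study day = 7 × week + 1, so Week 36 is Day 253 and Week 68 is Day 477, as the column headers state.
- 477 − 253 = 224 days; 224 / 7 = 32 weeks; 32 / 12 = 2.7 times the stated interval.
- Visit windows are ±3 days to Week 36 and ±7 days afterwards. Shortest: (477 − 7) − (253 + 3) = 214 days (30.6 weeks). Longest: (477 + 7) − (253 − 3) = 234 days (33.4 weeks).

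The qualifier that the interval is approximate cannot absorb a factor of 2.7.

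**3. Tests at stake.** Counting on from Week 36 in steps of 12 gives Weeks 48 and 60 before Week 68, so about two tests per covered subject are unmarked. Neither week is a scheduled site visit; the scheduled visits inside the interval are Weeks 44 and 56. A site following the footnote therefore has to choose its own timing.

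**4. Country lists side by side.**

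| Place | Countries named, besides local mandate |
|---|---|
| Section 5.3.1.1 and the Figure 2 note | China, Japan, South Korea |
| Appendix C footnote y | China, Japan, South Korea |
| Exclusion criterion 5 (entry PCR) | China, Japan, South Korea |
| Table 2 footnote e | China, Japan |

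**5. Entry PCR for an unvaccinated HBs Ab+, HBc Ab- subject.**

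- The first sentence of the Section 5.3.1.1 bullet, taken alone, requires no PCR.
- If its later parenthesis means unvaccinated subjects and, in addition, wherever mandated, PCR is required in every country. Exclusion criterion 5 does not ask for that.
- If it means unvaccinated and in a mandating location, PCR is required only there. That is close to exclusion criterion 5, but the bullet still does not name the three countries that the criterion names.

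**The case against.** The strongest reply is that the protocol's requirement is not in doubt. Footnote y is attached to the row label and so governs the whole row, Section 5.3.1.1 repeats it, and unscheduled testing is allowed. On that view only some grid marks are missing. This stands in part. A reader might infer that monitoring lapses for 32 weeks, and the documents do not show that: the 12-week text still binds, HBc Ab+ subjects keep the Table 4 trigger, and ALT/AST is drawn at Weeks 44 and 56 with rules that apply to all subjects. What the reply does not remove is the contradiction between grid and footnote. The unscheduled-visit wording is permissive and does not fill the gap.

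Three other stronger readings are tempting and also fail. One is that subjects are admitted on condition of later retesting; Section 5.3.1.1 makes entry depend on a negative HBV DNA result at Screening. Another is that all subjects with hepatitis B antibodies are affected; the rule is limited by country or mandate and has the vaccination exemption. The third is that the country and entry conflicts cause the gap; they are separate matters.

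On those two conflicts the reply has some force. Table 2 footnote e includes local mandates, so it may simply be an outdated list. The entry bullet can be read as a general rule with an exception, and it refers to Figure 2, whose diagram is not available here and might settle it.

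Finally, timing. SAP Section 11.1 (July 2021) reports Period 1 reporting as complete, and the Amendment 8 synopsis is dated December 2023, so enrolled subjects were past Week 68 by then. For them a grid correction is retrospective.

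**Conclusion.** The point holds as a contradiction within an operative safety schedule. For subjects under the retest rule, the grid leaves one 32-week unmarked interval (30.6 to 33.4 weeks with visit windows) against a stated interval of about 12 weeks. The consequence, about two missed tests per covered subject, assumes a site that works from the grid alone; the documents do not say how sites or laboratory kits were set up. The number of covered subjects is not stated.

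The omission of South Korea from Table 2 footnote e is a plain mismatch with Section 5.3.1.1 and footnote y, and it bears on any retesting still to be done up to Week 260. The entry rule is ambiguous rather than clearly contradictory, with the caveat about the Figure 2 diagram.

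**What to change.** Reconcile the passages; the sponsor decides which version is intended.

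- Bring the Appendix C hepatitis row, footnote y and Section 5.3.1.1 into agreement, so that the grid and the text give the same retest interval between Week 36 and Week 68.
- Use one country list in Table 2 footnote e, footnote y and Section 5.3.1.1.
- Make exclusion criterion 5 and the HBc Ab-negative bullet of Section 5.3.1.1 give one answer on PCR before entry for an unvaccinated HBs Ab+, HBc Ab- subject.
- For subjects already past Week 68, check whether retests were done between Weeks 36 and 68 and report what is found.

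The cost is wording, that check of existing records and possibly a few added PCR samples in the covered subgroup. Whether those would need separate blood draws is not stated for scheduled visits; Table 4 asks for a separate sample when the test is triggered by ALT/AST.

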Appendix D. Study Activities – Optional Samples for Exploratory Research or Validation Studies

	SCR D – 35	BL D	Wk 2	Wk 4	Wk 8 D	Wk 12 D	Wk 16	Wk 20 D	Wk 24	Wk 28	Wk 32 D	Wk 36	Wk 44 D	Wk 56	Wk 68 to Wk 248 (Every 12 Wks) D 477 to	Wk 260 or PD
Activity	to D – 1	1	15	29	57	85	113	141	169	197	225	253	309	393	D 1737	1821
Pharmacogenetic Sample ^{a,b}		X														
Epigenetic Sample ^{a,b,c}		X	X			X										
Transcriptomic and Epigenetic Sample ^{a,b,c}		X	X			X										
Proteomic and Targeted Protein Investigations Sample (Serum) ^{a,b,c,d}		X	X			X										
Proteomic and Targeted Protein Investigations Sample (Plasma) ^{a,b,c,d}		X	X			X										
Proteomic and Targeted Protein Investigations Sample (Urine) ^{a,b,c,d}		X	X			X										

BL = Baseline Visit; D = Day; F/U = Follow-up; PD = Premature Discontinuation; SCR = Screening Visit; Wk = Week

- b. Optional with signed ICF: if the ICF is not signed, samples for exploratory research or validation studies will not be collected.
- c Subjects are preferred to have been fasting approximately 8 hours prior to collection.
- d. An effort should be made to collect prior to dosing.

[figure not shown]
a. Based on the value of the different technologies, samples may also be used to assess other biomarker signatures, including but not limited to metabolomics, lipidomics and other approaches. Samples may be used for assay of study drugs if needed.

Appendix E. Latent TB Risk Assessment Form Example

- 1. Have you or an immediate family member or other close contact ever been diagnosed or treated for tuberculosis?
- 2. Have you lived in or had prolonged travels to countries in the following regions:
 - Africa
 - Eastern Europe
 - Asia
 - Russia
 - Latin America
 - Caribbean Islands
- 3. Have you lived or worked in a prison, refugee camp, homeless shelter, immigration center, or nursing home?
- 4. Have you, or an immediate family member, had any of the following problems for the past 3 weeks or longer:
 - Chronic Cough
 - Production of Sputum
 - Blood-Streaked Sputum
 - Unexplained Weight Loss
 - Fever
 - Fatigue/Tiredness
 - Night Sweats
 - Shortness of Breath

From: http://www.mayoclinic.org/diseases-conditions/tuberculosis/home/ovc-20188556 http://www.in.gov/fssa/files/Tuberculosis Questionnaire.pdf

Appendix F. Injection Instructions – Sample Pre-Filled Syringe

Injection Instructions – Sample Pre-Filled Syringe

Subject Instructions

0.8 mL dose

(Administered as a single dose-pre-filled syringe)

[figure not shown]
Protocol M15-572

Tables of Contents

Dosing Schedule

General Information & Supplies

Injection Procedures

Study Drug Dosin	ng Schedule	
Subject Number:		

You will require subcutaneous (SC) injections during the study. You will receive a kit each visit containing 2 syringes.

[figure not shown]
You will receive the following number of injections during this study:

- Baseline visit (the first visit to receive study medication for this study) you will receive 1 injection at the clinic (self-administer or receive help from site staff).
- You will receive either active study medication or placebo every other week throughout the blinded study period. You or a trained designee will inject your study drug.
- After all subjects have completed the blinded period you will only receive SQ injections if you continue on open-label adalimumab.

You should complete your injections the same day and approximately the same time every other week. If you forget to inject your study drug on your regularly scheduled dosing date, you should inject the forgotten dose as soon as you remember the dose was missed up to the day before the next scheduled dose. Two injections should not be administered on the same day.

If you experience a study drug interruption of > 2 consecutive missed doses during the first 24 weeks or > 3 consecutive missed doses after Week 24, you should notify your study site physician, and you should be discontinued from study drug. If study drug treatment is interrupted or withdrawn in Periods 1 or 2, study drug administration must be stopped.

Study drug kits containing 2 syringes will be provided for at home dosing, as needed.

[figure not shown]
Please return all used and unused syringes, the sharps container and empty boxes to the clinic on your next visit. Used syringes should be placed in the special Sharps container provided. All unused syringes should be returned in the original box.

If an injection is missed or something occurs where the full dose cannot be injected, contact your study center immediately for further instructions. Please record any missed doses on your subject dosing sheet.

Remember to complete your dosing sheet after each injection and to call the doctor's office if you are having problems administering your study medication.

General Information

- Pre-filled syringes with study medication will be labeled "Adalimumab or Placebo" during the blinded period and "Adalimumab" during the open label period.
- Store all pre-filled syringes in your refrigerator at 36°F to 46°F (2°C to 8°C) in the original container until it is used. NOT in the freezer. Should the syringes accidentally become frozen, call your study doctor's office.
- Protect the study medication from light.
- When traveling, study medication should be stored in a cool carrier with an ice pack.
- Do not use a prefilled syringe if the liquid is cloudy, discolored, or has flakes or particles in it.
- Do not drop or crush the study medication. The prefilled syringe is glass.
- Study medication should be taken at about the same time of day, on the same day of the week as directed by your study doctor.
- USE A NEW SYRINGE EVERY INJECTION DAY. There may be medication left in the syringe. **DO NOT RE-USE**.
- Save all study medications. *Pre-filled syringes* (used and unused) & empty boxes must be returned to the study center at each visit. Used syringes will be disposed of in a sharps container provided to you.

- Call your doctor IMMEDIATELY if you experience any itching, hives, shortness of breath, or any symptom that has you concerned. If you are unable to reach your doctor or if you experience life-threatening symptoms call, or proceed to your nearest emergency room.
- Keep study medication, injection supplies, and all other medicines out of the reach of children.

Injection Procedures (PFS)

[figure not shown]
1. Setting up for an injection

- Find a clean flat surface.
- Do not use if the seals on the carton are broken or missing. Contact your study doctor's office if the seals are broken.
- Take one kit with the prefilled syringe(s) of study drug from the refrigerator.

 Do not use a prefilled syringe that has been frozen or if it has been left in direct sunlight.
- Return any unused syringe(s) to the refrigerator.
- You will need the following items for each dose:
- study medication in pre-filled syringe(s)
- alcohol prep(s)
- cotton ball(s) or gauze pad(s)

[figure not shown]
If you do not have all of the items you need to give yourself an injection, call your study physician. Use only the items provided in the box your study drug comes in.

[figure not shown]
- Make sure the liquid in the prefilled syringe is clear and colorless. Do not use a prefilled syringe if the liquid is cloudy or discolored or has flakes or particles in it.
- Have a special sharps (puncture proof) container nearby for disposing of used needles and syringes.

For your protection, it is important that you follow these instructions.

2. Choosing and preparing an injection site

- Wash and dry your hands well
- Choose a site on the front of your thighs or your stomach area (abdomen). If you choose your abdomen, you should avoid the area 2 inches around your belly button (navel).
- Choose a different site each time you give yourself an injection. Each new injection should be given at least one inch from a site you used before.
 - **Never** inject into areas where the skin is tender, bruised, red or hard or where you have scars or stretch marks.
- If you have psoriasis, you should try not to inject directly into any raised, thick, red or scaly skin patches or lesions.
- You may find it helpful to keep notes on the location of your injection sites.
- Wipe the injection site with an alcohol prep (swab) using a circular motion.
- Do **not** touch this area again until you are ready to inject.

3. How to prepare your study drug dose for injection with a Prefilled Syringe

- Hold the syringe upright with the needle facing down.
- Check to make sure that there is liquid in the pre-filled
- The top of the liquid may be curved.
- If the syringe does not have liquid, do not use that syringe and call your study doctor.

[figure not shown]
If the syringe does not have the correct amount of liquid, do not use that syringe. Call your study doctor.

- Remove the needle cover taking care not to touch the needle with your fingers or allow it to touch any surface.
- Turn the syringe so the needle is facing up and slowly push the plunger in to push the air in the syringe out through the needle. If a small drop of liquid comes out of the needle that is okay.
- Do not shake the syringe.

[figure not shown]
4. Injecting your study drug dose

- With your other hand, gently squeeze an area of the cleaned area of skin and hold it firmly.
- You will inject into this raised area of skin. Hold the syringe like a pencil at about a 45° angle (see picture) to the skin.
- With a quick, short, "dart-like" motion, push the needle into the skin.

[figure not shown]
- After the needle is in, let go of the skin. Pull back slightly on the plunger. If blood appears in the syringe it means that you have entered a blood vessel. Do not inject the study drug. Pull the needle out of the skin and repeat the steps to choose and clean a new injection site. Do not use the same syringe. Dispose of it in your special sharps container. If no blood appears, slowly push the plunger all the way in until all of the study drug is injected.
- When the syringe is empty, remove the needle from the skin keeping it at the same angle it was when it was pushed into the skin.
- Press a cotton ball or gauze pad over the injection site and hold it for 10 seconds. Do not rub the injection site. You may have slight bleeding. This is normal.
- Dispose of the syringe right away into your special sharps container.

